There were approximately 325,000 IUD insertions identified during the time frame of the validation/feasibility study (i.e., end date, 30 September 2015), and approximately 65% of those occurred after at least 12 months within the data source. In approximately 90% of IUD insertions, this was the first observed insertion for each woman. Approximately 30% of women were identified as having an IUD inserted within the first 52 weeks postpartum. Based on these results and assumptions—approximately three additional years of data more than the validation study and allowing for a loss of approximately 15% of the insertions due to missing data and the propensity score trimming process (Section 9.7.1.3.2)—the number of first insertions of an IUD available through June 2018 from the four health care systems is anticipated to be approximately 225,000, with breastfeeding status available for approximately 60,000. For the two primary objectives related to the risk of uterine perforation, the power of the study is calculated for differences in the estimated risk of uterine perforation with respect to (1) breastfeeding status at the time of IUD insertion and (2) time interval of the IUD insertion following delivery. The null hypothesis to be tested for primary objective 1 is that the natural logarithm of the adjusted summary perforation hazard ratio for breastfeeding versus not breastfeeding at the time of IUD insertion is equal to 0. Using information from validation study, the expected allocation ratio of breastfeeding versus not breastfeeding is 60:40 for this objective. Three null hypotheses to be tested for primary objective 2 are that the natural logarithm of the adjusted summary perforation hazard ratio for early (i.e., ≤ 6 weeks postpartum, > 6 and ≤ 14 weeks, > 14 and < 52 weeks) versus later (i.e., > 52 weeks) postpartum IUD insertion is equal to 0. Based on information from the validation study, the expected allocation ratio of the corresponding postpartum period categories is 5:20:5:70 for this objective.

Power calculations for the expected number of IUD insertions were performed using PASS 14 software (NCSS, LLC, Kaysville, Utah) for a two-sided test of the hazard ratio (Schoenfeld, 1983). Table 4 indicates the power to detect various hazard ratios at the two-sided $\alpha = 0.05$ significance

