level based on a perforation risk of 1.3 per 1,000 insertions and the percentage of insertions expected for the exposure groups of interest, i.e., breastfeeding versus not breastfeeding and early versus late postpartum insertion for the two cutpoints of interest.

Table 4. Power to detect hazard ratio for uterine perforation based on anticipated number of intrauterine device insertions and exposure group allocation

Exposure groups	Number of insertions expected	Allocation % (exposed: unexposed)	Hazard ratio that can be detected (% power)				
			1.5	1.75	2.0	2.25	2.5
Primary objective, 1: Breastfeeding vs. not breastfeeding	60,000	60:40	42	68	85	94	98
Primary objective, 2: Categories of postpartum insertion timing: ≤ 6 weeks vs. > 52 weeks, including women without a recorded delivery within the past 52 weeks	168,750	5:70	32	54	73	85	92
Primary objective, 2: Categories of postpartum insertion timing: > 6 and ≤ 14 weeks vs. > 52 weeks, including women without a recorded delivery within the past 52 weeks	202,500	20:70	78	97	> 99	> 99	> 99
Primary objective, 2: Categories of postpartum insertion timing: > 14 weeks and ≤ 52 weeks vs. > 52 weeks, including women without a recorded delivery within the past 52 weeks	168,750	5:70	32	54	73	85	92

Table 5 displays the power to detect various hazard ratios at the two-sided $\alpha = 0.05$ significance level for the risk of perforation among LNG-releasing versus copper IUDs based on a perforation risk of 1.3 per 1,000 insertions and the percentage of insertions expected for the exposure groups of interest, i.e., timing of postpartum insertion and breastfeeding versus not breastfeeding.*

* These numbers are provided per the FDA request in the letter of 18 May 2016 to address the request to account for “sufficient number of users of both types of IUDs to allow secondary analyses of the comparative safety of LNG IUSs vs. copper IUDs with regard to early postpartum insertion and breastfeeding status at the time of insertion.” These power calculations are not necessarily directly linked to objectives, but rather indicate that adequate data are likely to be available to characterize comparative safety of LNG IUSs and copper IUDs.

Table 5. Power to detect hazard ratio for uterine perforation for LNG versus copper IUDs based on anticipated number of intrauterine device insertions and an 80% (LNG) versus 20% (copper) exposure group allocation

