Propensity scores will be used to measure the probability of being "exposed" given specified covariates. The propensity scores will be developed with respect to the outcomes being assessed

within this study and thus is not outcome blinded. This is a variable selection technique that elicits good results for propensity score models (Brookhart et al., 2006).

The results of this study are dependent on accurate capture of data and definitions of variables. Since variables will be determined from diagnosis codes (ICD-9-CM, ICD-10-CM*), Current Procedural Terminology codes, medication codes (National Drug Codes), and clinical notes (i.e., via NLP) there is a possibility of misclassification. Algorithms for the outcome variables, uterine perforation and IUD expulsion, have been validated in these four databases prior to use of ICD-10-CM coding. No formal validation of the algorithms with ICD-10-CM codes to identify uterine perforation or IUD expulsion will be done. However, the rates of these outcomes will be reviewed prior to and after the implementation of ICD-10-CM coding to ensure consistency over time. For variables that have not been validated in these databases, algorithms validated in other data sources (e.g., administrative claims) will be used to identify conditions and medication dispensing, when available. In addition, the study team will develop and share conceptual definitions across data sources to standardize approaches to data capture.

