6.3.3 Impact of Transition From ICD-9-CM to ICD-10-CM²

The results of this study are dependent on accurate capture of data from source files based on definitions of variables in this study. Since variables will be determined from diagnosis codes (ICD-9-CM, ICD-10-CM), Current Procedural Terminology codes, medication codes (National Drug Codes), and clinical notes (e.g., via natural language processing software) there is a possibility of misclassification. Algorithms for the outcome variables (uterine perforation and IUD expulsion) have been validated in these four databases prior to use of ICD-10-CM coding. No formal validation of the algorithms with ICD-10-CM codes to identify uterine perforation or IUD expulsion will be performed. However, the rate of these outcomes will be reviewed before and after implementation of ICD-10-CM coding to ensure consistency over time. Specifically, 01 October 2015 is the date of transition from ICD-9-CM to ICD-10-CM. The “before” time period will be defined as 01 October 2014 through 30 September 2015, and the “after” time period will be defined as 01 October 2015 through 30 September 2016. The number of patients with an outcome in each time period and the number of patients enrolled in each time period will be reported by data source research partners. The percentage of patients with an outcome among enrolled patients in each time period will be calculated. This analysis will be conducted using the “complete study population” defined in Section 5.1. The count and percentage will be reported for each outcome before and after the transition in the pooled data and by data source (planned Analysis Table 34.1).

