RI	xx	xx (xx.x)	xx (xx.x)	xx	xx (xx.x)	xx (xx.x)

[figure not shown]
IUD = intrauterine device.

Generated using xxxx.sas on xxxxxxxx.

[figure not shown]
Programming note 1: Research partners will provide counts for this table.

9.6 Illustration of Continuous Enrollment and Look-Back Time for Kaiser Permanente Sites (KPNC, KPSC, and KPWA)

[figure not shown]
Scenario 1. One IUD Insertion With No Uterine Perforation or IUD Expulsion

Scenario 2. One IUD Insertion With One Uterine Perforation

Scenario 3. Two IUD Insertions, With One IUD Expulsion and One Perforation

Note: if the beginning date of the study period is within the continuous enrollment period (illustrated in the above figures), the beginning date of the study period will be used as the beginning of continuous enrollment. Similarly, if the end date of the study period is within the continuous enrollment period, the end date of the study period will be used as the end of the continuous enrollment.

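### The one committed check of the outcome algorithms under ICD-10-CM is a one-year before/after percentage without person-time or interval, too imprecise to show moderate changes in perforation capture

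*SAP*

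**What the plan says.** Protocol Section 9.9 states that the perforation and expulsion algorithms were validated before ICD-10-CM coding and will not be formally validated under it. It offers instead that "the rates of these outcomes will be reviewed prior to and after the implementation of ICD-10-CM coding to ensure consistency over time".

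SAP Section 6.3.3 makes this specific. The windows are 1 October 2014 to 30 September 2015 and 1 October 2015 to 30 September 2016, in the complete study population. For each, "The percentage of patients with an outcome among enrolled patients in each time period will be calculated". Counts and percentages go into Table 34.1, pooled and by data source. Table Layout 13 prints percentages to one decimal and notes that "Research partners will provide counts for this table". No person-years, confidence interval, test or tolerance is specified.

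Elsewhere the plan takes a different line. Protocol Section 9.7.1.2.1 chooses crude incidence rates over incidence proportions because women contribute different amounts of time at risk, and SAP Section 4.1.2 gives the rate and its exact interval.

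**The concern.** Every outcome dated from 1 October 2015 comes from algorithms never tested under the codes then in use. If capture changed at the switch, the primary models would combine two outcome definitions. A fall in positive predictive value (PPV), for example, would add false positives and tend to pull the hazard ratios towards 1. Protocol Section 9.9 says that missing a real perforation risk is the error the sponsor most wants to avoid.

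The before/after table is what a reader will rely on to rule this out. A percentage of enrolled patients mixes new and long-standing users with different time at risk. Without an interval, two similar small percentages will be read as consistent whether or not the data could have shown a difference.

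**Working it through.** **1. Reproducing the plan's own figure.** The documents give no precision for this check, so the inputs are tested on Protocol Table 4. Its power is at a "level based on a perforation risk of 1.3 per 1,000 insertions". For objective 1, 60,000 × 0.0013 = 78 events, and "the expected allocation ratio of breastfeeding versus not breastfeeding is 60:40 for this objective". Schoenfeld power at HR 2.0 is Φ(√(78 × 0.6 × 0.4) × ln 2 − 1.96) = 85%, as stated. The other entries for both primary objectives also reproduce.

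**2. Coverage.** From 1 October 2015 to 30 June 2018 is 1,004 days. The after window has 366, so 638 days (64%) lie outside the check.

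**3. Insertions per year.** Protocol Section 9.5: "There were approximately 325,000 IUD insertions identified during the time frame of the validation/feasibility study (i.e., end date, 30 September 2015", the last day before the switch). Of these about 65% had 12 months of look-back and about 90% were first insertions.
- 325,000 × 0.65 × 0.90 = 190,125. After the 15% loss allowance, 161,606.
- The total "from the four health care systems is anticipated to be approximately 225,000, with breastfeeding status available for approximately 60,000". So 225,000 − 161,606 = 63,394 fall in the ICD-10 era (28%), or about 23,000 a year over 2.75 years.
- Before the loss allowance: 225,000/0.85 − 190,125 = 74,581, or about 27,000 a year.

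**4. Perforations per window.**
- New insertions only: 23,000 to 27,000 × 0.0013 = 30 to 35.
- Adding later events needs assumptions not in the documents: 24,000 insertions a year, 20% of users stopping each year, follow-up capped at 5 years, and 0.2 to 1.3 perforations per 1,000 person-years after year 1. Years 2 to 5 then hold 24,000 × (0.8 − 0.8⁵)/0.223 ≈ 50,800 person-years, hence 10 to 66 events. Added to 31 in year 1, this gives about 41 to 97, or roughly 40 to 100.

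**5. What the check can show for perforation, pooled (two-sided 0.05).** If the true ratio is 1, the 95% CI factor is exp(1.96√(2/e)) for e events per window. For e = 40 to 100, the ratio detectable with 80% power is exp(±2.8√(2/e)). For new insertions, a two-proportion power calculation at 0.13% was used.

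| Events per window | CI factor | Rise detectable with 80% power | Fall detectable with 80% power |
|---|---|---|---|
| 30–35 | 1.66–1.60 | ≥ 1.87–1.79 | to ≤ 0.40–0.43 |
| 40 | 1.55 | ≥ 1.87 | to ≤ 0.53 |
| 100 | 1.32 | ≥ 1.49 | to ≤ 0.67 |

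With 30 to 35 events, power is 18–20% for a 25% fall, 61–68% for a halving, 41–47% for a 50% rise and 88–93% for a doubling.

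**6. By site.** Regenstrief had about 5,700 eligible insertions from 2001 to September 2015 (14.75 years), about 400 a year, so about 0.5 perforations per window.

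**7. Expulsion.** The documents give no rate. At assumed risks of 1 to 5% a year in 23,000 women, 80% power is reached for ratios of at most 0.76 to 0.89, or at least 1.28 to 1.12.

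**8. Display.** In new insertions the percentage is 0.13%, printed 0.1. A 60% loss of capture gives 0.052%, also printed 0.1. Over all enrolled users, under the step 4 assumptions (about 92,000 to 108,000 women per window), it is about 0.04 to 0.10%. At 0.04% the table prints 0.0, as it would with no capture at all. Only the count would reveal the difference.

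**9. Longer windows.** With 2.75 years on each side (about 63,000 new insertions and 82 perforations each), 80% power is reached at ≤ 0.61 or ≥ 1.49, against ≤ 0.40 or ≥ 1.87 with 23,000 per one-year window. Power for a 25% fall rises only from 18% to 40%.

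**10. Restricted primary analysis.** If events fall in proportion to insertions, objective 1 keeps 78 × (1 − 0.28) ≈ 56, and power at HR 2.0 is 72%. This is an upper bound, because follow-up is also cut.

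**The case against.** Four stronger readings are tempting, and the documents do not support them.

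- **That no meaningful change could be detected.** A doubling of perforation would be seen with about 90% power, and at the assumed risks pooled expulsion changes of roughly 11 to 28% are within reach.
- **That nothing else protects the outcome.** Outcomes also draw on physician notes (Protocol Section 4.6.2). Calendar year is a candidate propensity-score covariate (SAP Section 3.3). Protocol Section 9.9 allows calendar-time analyses, and Section 9.6.3 says one site may build an outcome review form. None of these is a committed test of the ICD-10-CM algorithms, but together they rule out calling the table the sole safeguard.
- **That most ICD-10 data are thrown away.** Only the check stops at September 2016. The main analyses run to about June 2018.
- **That the primary hazard ratios are biased.** The switch falls on both exposure groups at the same time. A shared change in sensitivity would largely cancel if calendar year is balanced, and Protocol Section 9.9 sees no reason for under-capture to differ by exposure. Attenuation from a lower PPV remains possible, but nothing in the documents shows or sizes it.

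Two practical objections stand and shape the remedy. Under SAP Section 3.7, footnote 1, actual dates stay at the sites and may be offset before transfer, so the coordinating centre may be unable to split follow-up at the switch itself. And comparing all follow-up since 2001 with 2015–2018 would confuse coding with device launches, site start dates and changes in practice, which short adjacent windows limit.

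The lack of formal validation is disclosed, and the FDA approved the protocol that states it. That does not make the check more precise.

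**Conclusion.** The concern holds as a weakness of the check, not as a demonstrated flaw in the primary analysis. The plan promises rates and has the method for them, but delivers a one-decimal percentage without person-time or interval, over 12 of about 33 ICD-10 months. For perforation it can reliably show only about a 1.5- to 1.9-fold rise or a fall of about 30 to 60%. Similar percentages in the two years would therefore not establish consistency.

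The 30 to 35 events follow from the protocol's figures, given even accrual after September 2015. The 40 to 100 rest on the assumed later rates and discontinuation. The power figures treat the two windows as independent. Even a precise ratio near 1 would not prove stable PPV, because lost sensitivity and added false positives can offset each other.

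**What to change.** In SAP Section 6.3.3, Table 34.1 and Table Layout 13:

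1. Report events, person-years and incidence rates per 1,000 person-years by coding era, split at 1 year since insertion. Give the before/after rate ratio with 95% CI, pooled and by site where counts allow.
2. Use windows of equal length on each side of 1 October 2015, about 2.75 years, running to the end of data. Keep the one-year windows as a secondary display to limit secular change.
3. Add a sensitivity analysis that repeats primary objectives 1 and 2 with insertions and follow-up ended at 30 September 2015.

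**Cost.** The four partners must supply era-specific person-years and events, plus a truncated follow-up time and event flag for each insertion. Weights must be re-estimated and balance rechecked for two models. The restricted run is less precise: at most about 72% power at HR 2.0 for objective 1, against 85%. This supplements validation of ICD-10-era cases and does not replace it.

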6.4 Safety Analysis

No additional safety analysis is planned.

6.5 Analysis of Representativeness

The study will include all eligible patients identified from KPNC, KPSC, KPWA, and RI. This will cover the following geographic regions in the United States: northern California, southern California, Washington, and Indiana. Summary statistics for demographics and other baseline characteristics of the study cohorts will be provided as described in Section 6.1.

² ICD-9-CM = *International Classification of Diseases, 9th Revision, Clinical Modification*;
ICD-10-CM = *International Classification of Diseases, 10th Revision, Clinical Modification*.

6.6 Additional Analyses Planned to be Reported Outside the Study Report

No additional analyses are planned.

7 Document History and Changes in the Planned Statistical Analysis

- Final statistical analysis plan (SAP) v1.0, dated 29 June 2018 – initial version, submitted to FDA.
- SAP v2.0, dated 24 October 2018
 - The methods for confounder- or bias-adjusted analyses (previously Section 6.5) was moved to Section 4.1.5 as requested by FDA.
 - Section 4.1.5 (previously Section 6.5) was updated to state that a covariate will be included in the propensity score model if there is “at least a 10% change” rather than “a 10% change.”
 - Section 4.1.5 (previously Section 6.5) was revised to include key potential confounders (breastfeeding status, postpartum timing, and IUD type) within the propensity score model (as independent variables when not the dependent variable). Changes were also made to Section 4.1.6 (previously Section 4.1.5) and 6.2.2.3 to incorporate this change. Section 4.1.8 and 4.1.11 were removed as they were no longer needed.
 - The name of the baseline covariate “colposcopy” was changed to “colposcopy and other cervical procedures.”

8 References

- Bayer HealthCare Pharmaceuticals Inc. Mirena (levonorgestrel-releasing intrauterine system) [prescribing information]. October 2015. Available at: http://www.accessdata.fda.gov/drugsatfda_docs/label/2015/021225s031lbl.pdf. Accessed October 14, 2016.

	Crude IR, cum. incidence (first insertion)	Adj. HR via weighting, crude HR (first insertion)	Adj. HR via weighting, crude HR (subsequent insertions)	Weighted IRR and IRD (at 1 year and 5 years), crude IRR and IRD (first insertion)	Adj. and crude HR within each level of the modifier (first insertion)
Breastfeeding (AS2)	10	20	26		30, modified by IUD type
4-level postpartum (AS1)	9	23	26		32, modified by IUD type
≤ 14 wks vs. > 14 weeks postpartum (AS1)	9	21	26		
≤ 36 wks vs. > 36 weeks postpartum (AS1)	9	22	26	25	
IUD type ^a (AS3)	11	24	26		
Menorrhagia (AS1)	12	27			
Overall (AS1, AS2, AS3)	8				

AS1 = Analysis Set 1: complete study population; AS2 = Analysis Set 2: breastfeeding status available;
 AS3 = Analysis Set 3: IUD type available; HR = hazard ratio; IR = incidence rate; IRD = incidence rate difference; IRR = incidence rate ratio; IUD = intrauterine device.

^a Aggregated analysis only, not by site.

9.3 Propensity Score Models Defined by Exposure and Outcomes of Interest

Model Number	Exposure (Dependent Variable of Propensity Score Model)	Outcome (Not Included in Propensity Score Model)	IUD Insertion	Covariate Selection	Objective Number
1	Breastfeeding status (yes vs. no)	Uterine perforation	First insertion	Yes	1 (primary objective) 29
2	Postpartum insertion (4 categories)	Uterine perforation	First insertion	Yes	2 (primary objective) 14 ^a 15 ^a 17 ^a 31
3	IUD type (LNG vs. copper)	Uterine perforation	First insertion	Yes	16
4	Menorrhagia (yes vs. no)	Uterine perforation	First insertion	Yes	19
5	Breastfeeding status (yes vs. no)	IUD expulsion	First insertion	Yes	20 30
6	Postpartum insertion (4 categories)	IUD expulsion	First insertion	Yes	23 21 ^a 22 ^a 25 ^a 32
7	IUD type (LNG vs. copper)	IUD expulsion	First insertion	Yes	24
8	Menorrhagia (yes vs. no)	IUD expulsion	First insertion	Yes	27
9	Interaction of breastfeeding and early vs. late postpartum (breastfeeding/ \leq 14 weeks; breastfeeding/ $>$ 14 weeks; no breastfeeding/ \leq 14 weeks; no breastfeeding/ $>$ 14 weeks [referent])	Uterine perforation	First insertion	Yes	28
10	Breastfeeding status (yes vs. no)	Uterine perforation	Subsequent insertions	No ^b	18
11	Postpartum insertion (4 categories)	Uterine perforation	Subsequent insertions	No ^b	18 ^a
12	IUD type (LNG vs. copper)	Uterine perforation	Subsequent insertions	No ^b	18
13	Breastfeeding status	IUD expulsion	Subsequent insertions	No ^b	26
14	Postpartum insertion (4 categories)	IUD expulsion	Subsequent insertions	No ^b	26 ^a
15	IUD type (LNG vs. copper)	IUD expulsion	Subsequent insertions	No ^b	26

IUD = intrauterine device; LNG = levonorgestrel.

- ^a Secondary objectives include dichotomization of “early” and “late” postpartum categories. Separate propensity score models will not be *developed* for these objectives. Rather, the propensity scores calculated with the four-category variable will be used. The propensity scores for dichotomous exposure groups will be calculated by collapsing multiple categories (e.g., propensity score for ≤ 14 weeks = propensity score for ≤ 6 weeks + propensity score for > 6 to ≤ 14 weeks).
- ^b Covariates and terms included in the final propensity score model for first insertions will be included in the propensity score model for subsequent insertions. Additionally, IUD insertion count (the sequential number) may be included in the propensity score model if it is not balanced across exposure groups for subsequent insertions.

